Potential participants will be screened for eligibility by telephone. Eligible participants will be invited to give informed consent and complete the baseline assessment in person at the first study visit. During this assessment, we will ask participants to practice using the e-cigarette and give them instructions to return with their used e-cigarettes at their next study visit. We will also train participants to use the text messaging system during the baseline visit. For the training, we will establish an interactive texting protocol that introduces participants to the messaging process and trains them how to respond. After being enrolled in the SMS program a sample of questions will be text messaged to the participants and responses will be solicited to establish an understanding of how data collection works. This protocol is based on [name] current research. (Furberg 2012, Harris 2013) The interactions will be fully automated and cover: 1) welcome to the intervention, 2) some example questions with practice answering them, and 3) information on how to contact project staff for additional support.

After the baseline assessment participants, will be asked to track their smoking behavior for three days prior to beginning to reduce. We will prompt participants to report cigarette use with a text message reminder 4 times a day at 4 hour intervals (e.g., how many cigarettes have you smoked in the past 4 hours). The first text message inquiry of the day will ask participants to report any cigarettes smoked since the last text message prompt. This is meant to capture any overnight cigarette or e-cigarette use. The time of day for delivering text messages will be tailored to the participant's schedule of waking and sleeping.

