We will send questions via text messages for a total of 24 days (3 days of baseline assessment of cigarette use and 21 days of dual use with e-cigarette). The first phase of data collection will include a three-day baseline assessment of the study participants' usual smoking pattern. This will begin the day after the baseline assessment. Participants will receive text messages approximately every 4 hours (4 times/day). The questions will only ask about cigarette use in the previous time period, mood and cravings (Table 2). We will wait until the study participant responds to the first message before sending each follow up message. Depending on the participant's answer to whether or not they have smoked a cigarette and/or E-cigarette in the previous time period, they might receive different combinations of questions. For example, there are 6 questions in the first message each day for the 3 day baseline assessment of cigarette use. However if the participant has not smoked any cigarettes in the previous time period, they will only receive 3 of the questions. Each question is sent to the participant only after the previous one receives a response.

During the intervention stage which will last 3 weeks, we will again send text messages 4 x/day. These messages will assess the following 1) number of cigarettes smoked in the previous time period, 2) use of e-cigarettes, 3) satisfaction with cigarettes and/or e-cigarette ("On a scale of 0-9 how pleasurable was the last [cigarette/E-cigarettes]?"), and 4) cravings ("On a scale from 0-9 how much do you want to smoke a CIGARETTE right now?"). The first text of the day will also ask how soon after waking participants smoked a cigarette and used an e-cigarette and if they used cigarettes, how much do they want to smoke fewer cigarettes than usual and how hard it would be to use E-cigs only. Questions about use of e-cigarettes will include the following: 1) how many separate times in the previous time period did you use your e-cigarette ("time" is defined as around 5 or more puffs or 5 or more minutes of use), 2) On average, how many puffs did you take with each use, and 3) How many minutes ago was your last E-cigarette puff? We will use numerical scales because our experience has demonstrated that this allows for more accurate data collection.

If subjects do not return any messages for a 24 hour period we will contact them by phone to assess if there is a problem with receiving the texts.

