Table 2. Text messages and schedule

Rule (based on answer to the first question)	Text	3 days baseline tracking cig use				Intervention period			
		1 st	2 nd	3 rd	4 th	1 st	2 nd	3 rd	4 th
	Since your last report: Did you smoke a cigarette and/or E-cigarette? [no=0; cig=1; Ecig=2; both=3]	X	X	X	X	X	X	X	X
	Thinking about this morning, how many minutes after waking did you smoke your first cigarette? (Text 9999 if you did not smoke any cigarettes today)				X				X
	Thinking about this morning, how many minutes after waking did you use your first E-cig? (Text 9999 if you did not use any E-cigs today)								X
	Thinking about TODAY only: Do you want to smoke fewer cigarettes than usual? [0=Not at all ; 9=Very, Very Much]					X			
	Thinking about TODAY only: How hard would it be to use E-cigs ONLY? [0=Not at all ; 9=Extremely]					X			
If used cig	Since your last report: How many cigarettes did you smoked?	X	X	X	X	X	X	X	X
If used cig	How many minutes ago did you smoke a cigarette? [Text "0" if your are currently smoking]	X	X	X	X	X	X	X	X
If used cig only	On a scale of 0-9 how satisfying was your last cigarette? [0=Not at all – 9=Extremely Satisfying]	X	X	X	X	X	X	X	X
If used e-cig	Since your last report: How many separate times did you use an E-cigarette?					X	X	X	X
If used e-cig only	On average, how many puffs did you take with each use?					X	X	X	X
If used e-cig	How many minutes ago was your last E-cigarette puff? [Text "0" if you are currently using an E-cigarette]					X	X	X	X
If used e-cig	On a scale of 0-9 how satisfying was your last E-cigarette? [0=Not at all – 9=Extremely Satisfying]					X	X	X	X
	On a scale of 0-9, how much do you want to smoke a CIGARETTE right now? [0=Not at all – 9=Very, Very much]	X	X	X	X	X	X	X	X
	Thank you for completing the survey.	X	X	X	X	X	X	X	X

Primary outcome: For Aim 3, the primary outcome will be reduction in CPD and we will summarize this data as the proportion of participants who achieve 50% reduction in CPD at 3 weeks. Smoking reduction will be measured by a combination of self-report, text message data and changes in CO and saliva cotinine between baseline and end of treatment (3 weeks).

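### The protocol's definition of one e-cigarette use is missing from the text participants receive, and Table 2 asks about puffs only when no cigarette was smoked

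*Combined protocol and SAP*

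**What the plan says.** The narrative under Text message assessment lists three questions on e-cigarette use for the intervention period. The first asks for the number of separate times, and a *time* "is defined as around 5 or more puffs or 5 or more minutes of use". The second is "2) On average, how many puffs did you take with each use". The narrative does not limit it to intervals without cigarettes.

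Table 2 gives the messages as sent:

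- The opening item of each report is "Since your last report: Did you smoke a cigarette and/or E-cigarette", coded for none, cigarette, e-cigarette or both. It has no threshold.
- The count item, sent whenever an e-cigarette was used, is "Since your last report: How many separate times did you use an E-cigarette". It has no threshold and no definition.
- The puffs item is "On average, how many puffs did you take with each use". Its rule is "If used e-cig only".

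Study Procedures describes baseline training in the text system, including "some example questions with practice answering them". It does not mention the definition of a *time*. The same section says that staff will "give them instructions to return with their used e-cigarettes at their next study visit". No measure listed in Data collection and Measures, Table 1 or the analysis section uses the returned devices.

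Aim 2 covers daily patterns of e-cigarette use, including dual use, for the 4.5% and placebo products. Data Analysis and Data Monitoring gives as an example a Pearson correlation across participants between average craving and e-cigarette use. It does not say which variable stands for e-cigarette use.

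**The concern.** The count of times is the main daily measure of how much the e-cigarette is used. If the protocol defines the unit one way and the message leaves it open, each participant has to supply a definition. Differences between people then mix real use with interpretation. That weakens the Aim 2 description and the craving correlation, which is itself a between-person analysis. It cannot be repaired afterwards, because no item records which definition was applied.

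The rule on the puffs item adds a second gap. The intervention period is described as 21 days of dual use, so intervals with both products are central to Aim 2. Those are the intervals in which the puffs item would not be sent.

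**Working it through.** The documents state no exposure figure that depends on this definition, so there is nothing to reproduce. The check compares the wording and then illustrates the possible size of the error.

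**1. One participant, two readings.** Take one interval with no cigarettes and two e-cigarette uses, each of 3 puffs and each under 5 minutes. The opening item is answered as e-cigarette use under either reading.

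- Narrative definition: 0 times, so average puffs per use has no meaning.
- Message as sent: 2 times, 3 puffs on average, 2 × 3 = 6 puffs.

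The duration matters. A 3-puff use lasting 5 minutes or more counts under both readings.

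**2. Possible size.** All inputs here are assumed: T = 10 uses; a share s of them brief (below both limbs of the definition), from 0 to 0.60; b = 1 to 3 puffs per brief use; f = 8 or 12 puffs per full use. True puffs = T × [s·b + (1 − s)·f]. The ratio is reported times × reported average puffs, divided by true puffs.

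| Reading followed | Ratio | Range | Extreme case |
|---|---|---|---|
| Threshold on count and average | (1 − s)f / [s·b + (1 − s)f] | 0.64 to 1.00 | s = 0.6, b = 3, f = 8: 32/50 = 0.64 |
| No threshold on either | 1 | 1.00 | none |
| Threshold on count only | 1 − s | 0.40 to 1.00 | s = 0.6: 0.40 |
| Threshold on average only | f / [s·b + (1 − s)f] | 1.00 to 2.22 | s = 0.6, b = 1, f = 12: 120/54 = 2.22 |

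The count of times alone is 1 − s of all uses where the threshold is applied (0.40 to 1.00), and 1.00 where it is not. The error can therefore go either way for puffs.

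**3. Intervals with both products.** A report coded as both meets the rule for the count item but, read literally, not the rule for the puffs item. The intervention period has 21 × 4 = 84 scheduled reports per participant. Every one coded as both yields a count and no puff average. The documents do not say how many to expect.

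**4. Returned devices.** The return instruction is given at baseline and names the next study visit. A further 2-week supply is handed out at week 1, and no return instruction is stated for week 3. The research assistant's checklist already covers handing out e-cigarettes, but the documents do not say that devices dispensed or returned are counted.

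**The case against.** A reader might infer that brief uses drop out of the data. The documents do not support that. The message as sent has no threshold, so a participant who follows it counts every use. Brief uses are lost only if someone applies a definition that the message does not show. Even then, a low-puff use of 5 minutes or more still counts, and the puff limb is worded as approximate.

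A reader might also infer that the plan's exposure measure, times multiplied by puffs, is invalid. The plan never specifies that product or any variable for the amount inhaled. It also collects any use and minutes since the last puff in each report, time to first e-cigarette daily, and e-cigarette use at the visits.

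A third inference is that the comparison between arms is biased. If 60% of uses were brief in one arm and 30% in the other, total uses were equal and everyone applied the threshold, the ratio of counts would be 0.40/0.70 = 0.57. Every input to that is assumed. Both arms receive the same messages, and participants and research assistants are blinded.

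Finally, the amount of e-cigarette use is neither the primary outcome nor a listed secondary outcome, this is a 100-person pilot, and the rule on the puffs item may be a drafting slip or a way to save messages. These points limit the importance of the matter. They do not remove the mismatch: the narrative and Table 2 still disagree on both the unit and the rule, and nothing else in the documents settles either.

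**Conclusion.** The point holds as an unresolved inconsistency in how e-cigarette use is measured. The stated unit is not the unit asked for, and the puffs item has two different rules. The consequence is a count whose meaning may vary between participants, and a puff average that, on a literal reading of Table 2, is missing in dual-use intervals. The range of 0.40 to 2.22 shows only that the error could be material in either direction. It rests on assumed puffing patterns and on participants following different readings, and it is not an estimate for this trial. The effect is confined to Aim 2 and to analyses that use e-cigarette use, such as the craving correlation. The outcome of a 50% reduction in cigarettes per day and the planned 100 participants are untouched. The matter is worth correcting because the change is small and must be made before data collection.

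**What to change.** 1. Use one definition of a *time* in the narrative, the Table 2 message and the baseline text training. Either wording is defensible: *count any use, even 1 puff*, or the session threshold written into the message itself. With the any-puff wording and change 2, times × average puffs equals total self-reported puffs (not nicotine or volume inhaled), at the cost of comparability with studies that use a session threshold. State in the analysis section which variable represents e-cigarette use.
2. Change the rule on the puffs item so that it is sent in every interval with e-cigarette use, matching the count item and the narrative. This adds at most one message per report coded as both, so no more than 84 per participant. The message total under Payment for Participation should then be rechecked.
3. State that used devices are also returned at the week 3 visit. Record the number dispensed and the number returned used on the existing research assistant checklist, and report devices used by arm. This is a coarse check on the text data and cannot recover individual puffs. It costs two checklist lines.

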After tracking their cigarette use, all participants will receive a 20-30 minute behavioral counseling consultation with a trained tobacco counselor. The counseling session will be scheduled at the baseline visit. Counselors will review each participant's smoking pattern from the three days of tracking and offer tailored behavioral and environmental change strategies including specific smoking reduction strategy options, such as eliminating cigarettes at work, in the home, or least favorite or most favorite cigarettes of the day, carrying only those cigarettes needed for that day, dropping cigarettes associated with less intense triggers first, avoiding smoking triggers, using oral or manual replacements, and other strategies to manage urges. Since there is inadequate evidence that any one of these strategies was more effective than another, participants will be encouraged to choose those that are most appealing. Goal setting, and barriers identification will be used to help participants improve confidence in their ability to reduce the number of cigarettes they smoked (Josephs 2008).

In Summary, the baseline visit includes 1) completion of baseline survey, 2) registering subject on text messaging program, 3) have subject practice using the text message program, 4) proactive using e-cigarette 5) make appointment for counseling session and for returning to pick up e-cigarettes.

Participants will be encouraged to reduce the number of cigarettes smoked daily to at least 50% of the total number of cigarettes smoked per day at baseline. This level was selected a priori as a clinically significant measure of reduction and to be a substantial enough reduction to address partial compensatory smoking (Glasgow 2009). Participants will be encouraged to substitute the use of the e-cigarettes for each cigarette they eliminate in order to reduce nicotine withdrawal symptoms.

After the counseling session, they will return to [name] to pick up their supply of disposable electronic cigarettes to last one week. They will be reimbursed for travel expenses. At the end of week

Name of study: Assessing the use of electronic cigarettes (e-cigarettes) as a harm reduction strategy

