1 of ecig use, they will be asked to return to replenish the e-cigarettes for another 2 weeks and to complete a second in-person assessment. The final study visit will be 3 weeks post starting e-cigarettes. We will conduct in depth interviews with a random sample of 10 participants in each intervention arm at the week 1 and 3 study visits. The first visit will focus on a process evaluation of the data collection experience and satisfaction with e-cigarette use while Week 3 interviews will focus on gaining more in-depth understanding of their experience (ease of use, satisfaction) with the product over time, e-cigarette related outcome expectancies and norms and explore intentions to quit and/or continuing dual use of cigarettes and e-cigarettes.

Figure 2. Assessments and intervention period**Data collection and Measures**

Baseline assessments: *Demographic information:* age, race/ethnicity, gender, years of education, employment, income; *Smoking history:* number of cigarettes smoked per day, number of years as regular smoker; use of other tobacco products or e-cigarettes, number of previous attempts in the past 12 months; *Other smoking related information:* self-rated importance and confidence to reduce and to quit, intention/readiness to quit using the readiness ladder, risk perceptions about e-cigarettes and combustible cigarettes, social norms related to using cigarettes and e-cigarettes, an assessment of urges to smoke using the QSU-Brief survey, other household members smoking at home; and the *Behavioral factors in smoking dependence scale* (Glover 2005). We will also measure carbon monoxide and collect saliva for cotinine measurement at baseline and study visit 3.

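### The primary outcome is a 50% fall in cigarettes per day, but it is to be measured by an unspecified mix of survey, texts, CO and cotinine, and cotinine can classify equal reductions differently by arm

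*Combined protocol and SAP*

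**What the plan says.** The Primary outcome paragraph, after Table 2 of the combined protocol and SAP, names reduction in CPD as the primary outcome for Aim 3 and says "we will summarize this data as the proportion of participants who achieve 50% reduction in CPD at 3 weeks". The next sentence reads "Smoking reduction will be measured by a combination of self-report, text message data and changes in CO and saliva cotinine", with the change taken from baseline to the end of treatment.

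The other relevant text is as follows.

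- **Threshold.** Under Study Procedures, participants are encouraged to "reduce the number of cigarettes smoked daily to at least 50% of the total number of cigarettes smoked per day at baseline". Of this level the plan says "This level was selected a priori as a clinically significant measure of reduction". It is a threshold for cigarettes only.
- **Survey CPD.** The baseline smoking history includes "number of cigarettes smoked per day, number of years as regular smoker". Cigarette use is asked again at weeks 1 and 3. Table 1 words the item as the number per day on days when the person smokes.
- **Text CPD.** Texts run for "3 days of baseline assessment of cigarette use and 21 days of dual use with e-cigarette", four times a day, each asking "Since your last report: How many cigarettes did you smoked".
- **Biomarkers.** "We will also measure carbon monoxide and collect saliva for cotinine measurement at baseline and study visit 3". Table 1 connects CO and saliva with validated abstinence. The only CO level given is the 8 ppm entry criterion. No cotinine level is given.
- **Analysis.** Data Analysis and Data Monitoring mentions a generalized linear mixed model but does not say how the sources form the response variable.

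**The concern.** A responder proportion needs one yes-or-no rule per participant. Here the threshold, the measure and the time are fixed, but the route from four data streams to that yes or no is not. Three things are open: which CPD source decides, which baseline and which follow-up days are used, and what part CO and cotinine play.

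The biomarker question goes beyond missing detail. Participants are asked to replace cigarettes with an e-cigarette that contains nicotine in one arm and none in the other. Putting cotinine into responder status would therefore let the assigned product influence the outcome classification directly. The survey and text question matters because the two sources measure somewhat different things and need not agree for the same person. At stake are the pooled proportion that answers research question 2 and the fairness of the classification between arms.

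**Working it through.** **1. No planned figure to reproduce.** Number of Subjects gives 100 in total, 50 per arm, with no alpha, power, responder rate or dropout. No agreement between sources is stated either. Every rate below is therefore an assumption.

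**2. What each source can deliver.** Only the survey and the texts yield a cigarette count. Halving CPD cannot be read from CO or cotinine without a conversion, and none is given. The two count sources also differ. The survey asks about days on which the person smokes, while the texts add up counts over successive windows on all days. Each has its own baseline (visit survey, or three tracked days). The plan does not say which of the 21 text days make up week 3, or how a partly answered day becomes a CPD.

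**3. Cotinine by arm.** Take two participants at the entry minimum of 10 a day who both fall to 5 and use the e-cigarette in place of the other 5. Their CPD reduction is identical. The one on the 4.5% product still takes in nicotine from it; the one on placebo does not. A rule that also requires a cotinine fall could pass the second and fail the first. The documents give no data from which to size this.

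**4. Survey against text.** Assume two sources, each with responder probability p and latent normal correlation ρ. For p = 0.5:

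- both = 1/4 + arcsin(ρ)/(2π)
- either = 2p − both

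At ρ = 0.6, arcsin(0.6) = 0.6435, so both = 0.25 + 0.6435/6.2832 = 0.352 and either = 1 − 0.352 = 0.648.

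| ρ | both | either | gap (points) |
|---|---|---|---|
| 0.4 | 31.5% | 68.5% | 36.9 |
| 0.6 | 35.2% | 64.8% | 29.5 |
| 0.8 | 39.8% | 60.2% | 20.5 |
| 0.95 | 44.9% | 55.1% | 10.1 |

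At ρ = 0.6 with other rates, p = 0.3 gives 17.3% and 42.7%, and p = 0.6 gives 45.7% and 74.3%.

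**5. Comparison with sampling error.** The 95% half-width at p = 0.5 is 1.96 × √(0.25/100) = 9.8 points pooled and 1.96 × √(0.25/50) = 13.9 points per arm. The gap between rules is at least about as large as the pooled half-width, even at ρ = 0.95.

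**6. Choosing the source after unblinding.** I simulated 40,000 null trials at each ρ, with 50 per arm, p = 0.5 and a two-sided two-proportion z test at 0.05. One fixed source rejected in 5.5–5.9% of trials. Taking the smaller p-value of the two sources rejected in 10.8%, 10.3%, 9.8% and 9.0% at ρ = 0.4, 0.6, 0.8 and 0.95.

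**The case against.** The strongest reply is that the first sentence already fixes the endpoint as CPD, 50% and 3 weeks, and the second only describes measurement. Since CO and saliva are tied to abstinence in Table 1, they may be meant as supportive. That reading is available, and a reader who infers that the two sentences define two different events goes too far. But the text does not say that biomarkers are supportive, and this reading still leaves survey against text, the baseline and the window unsettled.

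Three further inferences are tempting and not supported.

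- **That this trial's result will be 35% or 65%.** Those figures follow from assuming 50% responders per source and ρ near 0.6. Moreover, if one source simply took precedence and both had the same rate, the expected pooled proportion would not move; only individual classifications would.
- **That the false-positive rate is 12–15%.** This comes from picking the best of four readings, one of which treats a third source as having its own 50% responder rate. If that source is a biomarker, no threshold exists from which to form it. The two CPD sources alone support about 9–11%, and only if the smaller p-value is always chosen.
- **That the rule will be chosen after the data are seen.** The documents show only that no rule is stated. It can still be fixed before unblinding.

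It also stands that this is a pilot with no stated alpha or power. Research question 3 and Aim 3 do compare the arms, but the Secondary outcomes paragraph calls arm differences in the primary and secondary outcomes an exploratory secondary aim. The false-positive argument is therefore secondary.

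**Conclusion.** The concern holds in a limited form. The plan fixes the threshold, measure and time of the primary outcome but not the deciding CPD source, its baseline, its follow-up days or the role of the biomarkers. Following the stated combination literally would bring cotinine into a CPD outcome when only one arm's product delivers nicotine. That could misclassify participants differently by arm, by an amount the documents do not allow one to compute.

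For the two CPD sources, the spread between requiring both and accepting either is about 10 to 37 points for ρ from 0.95 to 0.4, assuming 50% responders on each. The main consequences are for the pooled proportion and for differential misclassification. Inflation of the arm test is a lesser one. No stated sample-size figure is shown to be wrong. The change should be made, but it does not threaten the pilot as a whole.

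**What to change.** In the Primary outcome paragraph, delete the reference to a combination and state the following before unblinding.

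1. **One source, matched baseline.** Define responder status from a single CPD source, with follow-up and baseline both from that source. One example is mean text CPD over the last 7 e-cigarette days at or below 50% of the three-day text baseline. The choice of texts and of 7 days is the sponsor's to make; the documents favour neither source.
2. **Usable data.** State the minimum number of answered prompts for a usable day, and the number of usable days needed for a participant to be scored from texts.
3. **Fallback.** If survey CPD is used for participants without usable texts, compare week-3 survey CPD with baseline survey CPD, never with the text baseline.
4. **Sensitivity.** Name the other CPD source as a sensitivity analysis and report survey–text discordance by arm. This also serves the planned feasibility measure of consistency in tracking.
5. **Biomarkers.** Report CO and cotinine changes separately, by arm, as supportive outcomes outside responder status.

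The cost is a few sentences and one additional table, all from data already planned. The downside is that responder status is not biochemically supported.
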